### 5. **Dose Fractionation Schedules**

- Dose level 1: 30 Gy in 3 fractions over 5 days.
- Dose level 2: 54 Gy in 3 fractions over 5 days.

### 6. **Physics Planning**

- Type B or Monte Carlo algorithm is mandatory.
- Dose grid resolution on the final dose calculation must be  $\leq 2$  mm.

**Table A:** Contouring of normal tissue structures.

[figure not shown]
Spinal Canal PRV	The spinal canal will be contoured at least 10 cm above and below the extent of the PTV and taken to represent the cord. A centre dependent margin should be added to the canal to create the spinal canal PRV dependent on immobilization technique (e.g. 3 – 5 mm) on which the dose constraints should be assessed. This structure is used to assess both spinal cord and cauda equina dose constraints.
Brachial Plexus	Contouring, on head and neck windowing, will start at the neural foramina at the C4-C5 level and move caudally; the region from the lateral aspect of the spinal canal laterally to the small space between the anterior and middle scalene muscles will be contoured. At the levels at which no neural foramina are present, the space or soft tissue between the anterior and middle scalene muscles will be contoured. Contouring will continue in the space between the anterior and middle scalene muscles; Inferiorly the major trunks of the ipsilateral brachial plexus will be contoured by using the subclavian and axillary vessels as a surrogate. They will be contoured from the bifurcation of the brachiocephalic trunk into the jugular/subclavian veins (or carotid/subclavian arteries), following along and ending after the neurovascular structures cross the 2nd rib.
Lungs	Normal lung will consist of both lungs as one structure (including all inflated and collapsed regions of lung and excluding the proximal airways), contoured on lung windows, considered together as one organ (minus the GTV when treating lung lesions).
Trachea	Contouring of the proximal trachea should begin at least 10 cm superior to the extent of the PTV or 5 cm superior to the carina (whichever is more superior) and continue inferiorly to the superior aspect of the proximal bronchial tree.
Bronchial Tree	The proximal bronchial tree will include the most inferior 2 cm of distal trachea and the proximal airways on both sides. The following airways will be included according to standard anatomical relationships: the distal 2 cm of trachea, the carina, the right and left main stem bronchi, the right and left upper lobe bronchi, the intermedius bronchus, the right middle lobe bronchus, the lingular bronchus, and the right and left lower lobe bronchi. Contouring of the lobar bronchi will end immediately at the site of a segmental bifurcation.
Great Vessels	The great vessels (aorta and vena cava) will be contoured using mediastinal window to correspond to the vascular wall and all muscular layers out to the fatty adventitia. The great vessel should be contoured at least 10 cm above and below the extent of the PTV. For right sided lesions, the vena cava will be contoured, and for left sided lesions, the aorta will be contoured.
Oesophagus	The oesophagus should be contoured as a solid structure from the upper sphincter (cricoid level) down to the gastro-oesophageal junction using mediastinal windowing. The delineation limit is the outer wall of the oesophagus.
Heart and Pericardium	The heart will be contoured along with the pericardial sac using mediastinal windowing. The superior aspect is defined as the superior aspect of the pulmonary artery (as seen on coronal reconstruction of the CT) and the caudal border should be defined by the lowest part of the left ventricle's inferior wall that is distinguishable from the liver.
Chest Wall	The chest wall will be defined as the 2 cm rind of the ipsilateral hemi-thorax outside the thoracic cavity and contoured at least 5 cm above and below the PTV.

## 7. **Target Coverage, Maximum Dose, Conformity Parameters and OAR Dose Constraints**

- Target Coverage: Aim for the dose received by 95% and 99% of the PTV to be greater than 100% and 90% respectively ( $D_{95} \geq 100\%$  and  $D_{99} > 90\%$ ).
- Maximum Dose: This should ideally be within 110-140% (of the prescribed dose, 105-145% mandatory) and be located within the GTV. This is equivalent to prescribing to approximately the 70-95% isodose (relative to the maximum).
- Target Dose Conformity: Where possible the conformity constraints should be met (see Table B below).
- OAR dose constraints will be achieved for all patients (see Table C below).
- If the dose constraint for an OAR is not reached, the dose in the PTV will be reduced in order to meet the OAR constraint. Two approaches are possible:
- Reduced prescription dose: The prescribed dose can be reduced but to no less than 90% of the BED.
- Inhomogeneous PTV dose: In case of overlap of the PTV with OAR, the dose to the CTV (or ITV if applicable) can be maintained and the dose within the PTV may be reduced until the planned dose to the OAR meets the acceptable variation criteria for the OAR. The dose in 95% of the PTV should still at least be 80%.

## 8. **Image Guidance for Treatment Verification and Delivery**

- CBCT (or 4D CBCT imaging where appropriate and available) and on-line correction prior to each fraction will be performed with manual adjustment under direct visualization of the tumour if required.
- The position of critical OAR will be checked, especially the spinal cord and any changes in anatomy.
- Repeat CBCT scans will be considered after correction prior to treatment delivery and again after treatment delivery if clinically indicated for additional verification.

**Figure A:** Recommended definition of a **central thoracic lung lesion**: a lesion within 2 cm in all directions of any mediastinal critical structure, including the bronchial tree, oesophagus, heart, brachial plexus, major vessels, spinal cord, phrenic nerve, and recurrent laryngeal nerve.

**Table B:** Dose Conformity Requirements

PTV (cc)	R100		R50		D max (>2 cm from PTV) SBRT in 3 #	
	Optimal	Mandatory	Optimal	Mandatory	Optimal	Mandatory
<20	<1.25	1.25-1.40	<12	12-14	<35.1Gy	35.1-40.5Gy
20.1-40	<1.15	1.15-1.25	<9	9-11	<37.8Gy	37.8-43.2Gy
>40.1-60	<1.10	1.10-1.20	<6	6-8	<37.8Gy	37.8-43.2Gy
60.1-90	<1.10	1.10-1.20	<5	5-7	<37.8Gy	37.8-43.2Gy
>90.1	<1.10	1.10-1.20	<4.5	4.5-6.5	<37.8Gy	37.8-43.2Gy

R100 = Vol(100%)/Vol(PTV) = Ratio of prescription isodose volume to the PTV

R50 = Vol(50%)/Vol(PTV) = Ratio of 50% prescription isodose volume to the PTV

Dmax (>2 cm from PTV) = Maximum point dose at least 2 cm from the PTV in any direction

**Table C:** OAR Dose Constraints

OAR	Constraint	SBRT in 3 #	
		Optimal	Mandatory
Brachial Plexus	DMax (0.5 cc)	< 24 Gy	< 26 Gy
Normal Lungs (Lungs – GTV)	V 20 Gy	-	< 10%
	V 12.5 Gy	-	< 15%
Trachea and Proximal Bronchial Tree	DMax (0.5 cc)	< 30 Gy	< 32 Gy
Great Vessels	DMax (0.5 cc)	-	< 45 Gy
Heart	DMax (0.5 cc)	< 24 Gy	< 26 Gy
Oesophagus	DMax (0.5 cc)	-	< 25.2 Gy
Spinal Cord (Spinal Canal PRV)	DMax (0.1 cc)	< 18 Gy	< 21.9 Gy
	D 1.2 cc	< 12.3 Gy	-
Chest Wall	DMax (0.5 cc)	< 37 Gy	-
	D 30 cc	< 30 Gy	-
Skin	DMax (0.5 cc)	< 33 Gy	-
	D 10 cc	< 30 Gy	-

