## **8.2 Sample Size**

During the dose escalation phase a standard 3+3 design will be used to recruit patients into two lung SBRT dose cohorts, firstly dose level 1 and then dose level 2, and both given the same pembrolizumab fixed dose level. Each cohort will require a minimum of 3 and a maximum of 6 patients. This means that there will be a minimum of 6 and maximum of 12 patients required for dose escalation. There will then be an additional 12 patients in the expansion phase. This number has been arbitrarily chosen to get a better appreciation for the toxicity profile of the dose/treatment that maybe taken forward in a phase II study.

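### Table B's dose limit at 2 cm from the PTV is fixed in Gy at 65–80% of 54 Gy, so at dose level 1 (30 Gy) it is 117–144% of prescription and very unlikely to bind

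*Combined protocol and SAP*

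**What the plan says.** Appendix 3, item 5 gives two schedules: "Dose level 1: 30 Gy in 3 fractions over 5 days" and "Dose level 2: 54 Gy in 3 fractions over 5 days".

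Table B then sets three conformity metrics by PTV volume. Two are relative to the prescription: R100, and R50, which is the "Ratio of 50% prescription isodose volume to the PTV". The third, Dmax at more than 2 cm from the PTV, is the "Maximum point dose at least 2 cm from the PTV in any direction" and is given in Gy:

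| PTV | Optimal | Mandatory |
|---|---|---|
| under 20 cc | below 35.1 Gy | 35.1–40.5 Gy |
| all larger bands | below 37.8 Gy | 37.8–43.2 Gy |

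The column is headed for SBRT in 3 fractions, which describes both dose levels. Appendix 3 has no separate 30 Gy values and no scaling rule.

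Two provisions in item 7 bear on how much this matters. The status of the table is: "Target Dose Conformity: Where possible the conformity constraints should be met (see Table B below". The plan maximum is limited as follows: "Maximum Dose: This should ideally be within 110-140% (of the prescribed dose, 105-145% mandatory) and be located within the GTV".

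**The concern.** A conformity limit is meant to show that dose falls away outside the target. It can do so only if it lies below the prescribed dose by a sensible margin. The Dmax figures do that at 54 Gy. At 30 Gy every one of them is above the prescription, so a plan with poor remote fall-off would still pass.

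What is at stake is the quality control of treatment plans at dose level 1, and the use of one conformity standard for the two dose levels being compared. Section 8.2 states: "Each cohort will require a minimum of 3 and a maximum of 6 patients". The gap therefore touches 3 to 6 evaluable patients in Part A, plus any replacements under section 4.3. It would extend to Part B if 30 Gy were taken forward as the RP2D.

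**Working it through.** **Inputs.** Prescriptions of 30 Gy and 54 Gy (Appendix 3, item 5); Dmax, R100 and R50 limits (Table B); plan maximum ideally up to 140% and mandatorily up to 145% of prescription (item 7).

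**1. Limits as a share of prescription** (limit ÷ prescription)

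| Limit (Gy) | ÷ 54 Gy | ÷ 30 Gy |
|---|---|---|
| 35.1 | 65% | 117% |
| 37.8 | 70% | 126% |
| 40.5 | 75% | 135% |
| 43.2 | 80% | 144% |

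All four are exact round percentages of 54 Gy, so the column is reproduced as a 54 Gy table.

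**2. Comparison with the highest dose allowed anywhere in a 30 Gy plan**

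- Ideal maximum: 1.40 × 30 = 42.0 Gy.
- Mandatory maximum: 1.45 × 30 = 43.5 Gy.

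The 43.2 Gy limit for larger PTVs lies above the ideal maximum and 0.3 Gy below the mandatory one. A plan that meets the ideal maximum cannot breach 43.2 Gy at any point. The other three limits are below 42.0 Gy, but item 7 also places the maximum inside the GTV, so doses near these values are not expected 2 cm outside the PTV.

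**3. Where the isodoses fall.** Treat the PTV and the isodose volumes as concentric spheres, with radius r = (3V/4π)^(1/3). An isodose enclosing R times the PTV volume then lies r × (R^(1/3) − 1) beyond the PTV edge. At the upper R100 and R50 limits:

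| PTV (cc) | r (cm) | R100 | 100% isodose beyond PTV (cm) | R50 | 50% isodose beyond PTV (cm) |
|---|---|---|---|---|---|
| 20 | 1.68 | 1.40 | 0.20 | 14 | 2.37 |
| 40 | 2.12 | 1.25 | 0.16 | 11 | 2.60 |
| 60 | 2.43 | 1.20 | 0.15 | 8 | 2.43 |

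In these cases a point 2 cm out lies between the 100% and 50% isodoses. At 30 Gy that is 15–30 Gy, below the lowest Table B limit of 35.1 Gy. At 54 Gy it is 27–54 Gy, a range that contains all four limits, so the check can work there.

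Smaller PTVs or tighter R50 values bring the 50% isodose inside 2 cm: 1.88 cm for 10 cc at R50 = 14, and 1.98 cm for 60 cc at R50 = 6. The dose at 2 cm is then below 50% of prescription, and the fixed limit is slacker still.

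**4. Limits rescaled to 30 Gy**

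- PTV under 20 cc: 0.65 × 30 = 19.5 Gy and 0.75 × 30 = 22.5 Gy.
- Larger PTVs: 0.70 × 30 = 21.0 Gy and 0.80 × 30 = 24.0 Gy.

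All four fall within the 15–30 Gy range from step 3, so they could bind.

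**The case against.** The strongest reply is that nothing in Table B is miscalculated, and that an absolute ceiling which is slack at the lower dose is not in itself an error. Table C also uses absolute limits for both dose levels, and its 45 Gy limit for the great vessels exceeds the 43.5 Gy maximum allowed in a 30 Gy plan. This carries some weight: the defect is a missing specification for one dose level. The comparison with Table C is weaker than it looks, though. Table C holds organ tolerances, which are naturally absolute. Table B is a conformity table whose limits vary with PTV volume and whose other two metrics scale with prescription.

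A second reply is that other rules already do the protective work, and this largely stands. R100 and R50 still bind at 30 Gy. Central lesions are excluded from the target definition. The mandatory Table C limits for cord (21.9 Gy), oesophagus (25.2 Gy), heart and brachial plexus (26 Gy each) and central airways (32 Gy) are all below 35.1 Gy, and unlike Table B the organ limits are required in every patient. Great vessels and chest wall are less well covered. R50 is a volume ratio and does not cap a single remote point, which is the purpose of the Dmax column.

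Third, the spherical model is idealised: it cannot represent uneven spill, which is what a point maximum detects. That is why the claim is that the limit is very unlikely to bind, and not that it never could.

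Finally, the reach into Part B is uncertain. Section 3.2 says expansion follows unless the MTD is dose level 1, while other text in sections 3.2 and 3.2.1 allows expansion at the previous dose level.

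**Conclusion.** The point holds, as a minor one. The Dmax limits are 65–80% of prescription at 54 Gy and 117–144% at 30 Gy, and nothing in the protocol rescales them. Applied as written, the remote-dose check adds almost nothing at dose level 1.

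The conclusion rests on one inference and one approximation. The inference is that the limits were set for 54 Gy; the protocol does not say so, but four exact round percentages make coincidence implausible. The approximation is the spherical geometry. The ratios themselves, and the comparison with the permitted plan maximum, need neither.

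Direct harm to patients is unlikely, and the sample size and the analysis are unaffected.

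**What to change.** State the Dmax column in Table B as a percentage of the prescribed dose:

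- PTV under 20 cc: optimal below 65%, mandatory 65–75%.
- Larger PTVs: optimal below 70%, mandatory 70–80%.

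The 54 Gy values stay as they are. At 30 Gy the column becomes below 19.5 Gy and 19.5–22.5 Gy for small PTVs, and below 21.0 Gy and 21.0–24.0 Gy for larger ones. The 30 Gy figures are an extrapolation of the 54 Gy percentages and have no other source in the protocol, so the radiotherapy QA group should confirm them before they are adopted.

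The cost is an edit to one column of one appendix table, and slightly tighter planning at 30 Gy.

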## **11.4 Appendix 4 - Common Terminology Criteria for Adverse Events V4.0 (CTCAE)**

The descriptions and grading scales found in the revised NCI Common Terminology Criteria for Adverse Events (CTCAE) version 4.0 will be utilized for AR reporting. (<http://ctep.cancer.gov/reporting/ctc.html>)

### **1. Quick Reference**

The NCI Common Terminology Criteria for Adverse Events is a descriptive terminology which can be utilized for Adverse Event (AE) reporting. A grading (severity) scale is provided for each AE term.

### **2. Components and Organization SOC**

System Organ Class, the highest level of the MedDRA hierarchy, is identified by anatomical or physiological system, etiology, or purpose (e.g., SOC Investigations for laboratory test results). CTCAE terms are grouped by MedDRA Primary SOCs. Within each SOC, AEs are listed and accompanied by descriptions of severity (Grade).

### **3. CTCAE Terms**

An Adverse Event (AE) is any unfavorable and unintended sign (including an abnormal laboratory finding), symptom, or disease temporally associated with the use of a medical treatment or procedure that may or may *not* be considered related to the medical treatment or procedure. An AE is a term that is a unique representation of a specific event used for medical documentation and scientific analyses. Each CTCAE v4.0 term is a MedDRA LLT (Lowest Level Term).

### **4. Definitions**

A brief definition is provided to clarify the meaning of each AE term.

### **5. Grades**

Grade refers to the severity of the AE. The CTCAE displays Grades 1 through 5 with unique clinical descriptions of severity for each AE based on this general guideline:

Grade 1 Mild; asymptomatic or mild symptoms; clinical or diagnostic observations only; intervention not indicated.

Grade 2 Moderate; minimal, local or non-invasive intervention indicated; limiting age-appropriate instrumental ADL\*.

Grade 3 Severe or medically significant but not immediately life-threatening; hospitalization or prolongation of hospitalization indicated; disabling; limiting self-care ADL\*\*.

Grade 4 Life-threatening consequences; urgent intervention indicated.

Grade 5 Death related to AE.

### **6. Activities of Daily Living (ADL)**

\*Instrumental ADL refer to preparing meals, shopping for groceries or clothes, using the telephone, managing money, etc. \*\*Self-care ADL refer to bathing, dressing and undressing, feeding self, using the toilet, taking medications, and not bedridden.

## 11.5 Appendix 5 - Identification, Evaluation and Management of immune related events of clinical interest (irECIs)

ECI	Grade	Action to be taken	Supportive Care
Pneumonitis –	Grade 1 (Asymptomatic)	
 
No action
 
	
 
Intervention not indicated
 

	Grade 2	
 
Report overdose and liver toxicity ECIs within 24 hours
 
Withhold pembrolizumab, may restart if Grade 1 or resolved within 12 weeks
 
Consider bronchoscopy and biopsy/BAL, ID Consult and frequent chest x-ray for monitoring.
 
Conduct in person evaluation twice a week
 
	
 
1-2mg/kg/day prednisone or equivalent.
 
Symptoms grade 1 or less, initiate steroid taper for no less than 4 weeks.
 
Permanently discontinue pembrolizumab if dose cannot be reduced to 10mg prednisone or less or equivalent per day within 12 weeks.
 

	Grade 3 and 4	
 
Report overdose and liver toxicity ECIs within 24 hours
 
Discontinue pembrolizumab
 
Hospitalise patient
 
Bronchoscopy with biopsy and/or BAL is recommended.
 
	
 
methylprednisolone 125mg IV.
 
Symptoms grade 1 or less initiate steroid taper for no less than 4 weeks 
 
Prednisone 1 to 2 mg/kg/day or dexamethasone 4mg every 4 hours
 
 
 
If IV steroids do not reduce initial symptoms within 48-72 hours treat with additional anti-inflammatory measures. At symptom relief discontinue anti-inflammatory and start steroid taper over 45-60 days. If symptoms worsen during this period refer to Section 6 and 7.
 

 
1st episode - May increase dosing interval by one week in subsequent cycles
 
2nd episode of - Pneumonitis, permanently discontinue pembrolizumab if upon re-challenge patient develops Pneumonitis ≥ Grade 2
 
			
Colitis	Grade 1 (Asymptomatic)	
 
No action
 
	
 
Intervention not indicated
 

–			
		
 
Report overdose and liver toxicity ECIs within 24 hours
 
Withhold pembrolizumab, may restart if Grade 1 or resolved within 12 weeks
 
Symptomatic treatment 
 
Consider GI consult & endoscopy to rule out colitis
 
 
 
	
 
Prednisone 1-2mg/kg/day or equivalent
 
Symptoms grade 1 or less, initiate steroid taper for no less than 4 weeks.
 
Permanently discontinue pembrolizumab if dose cannot be reduced to 10mg or less of prednisone or equivalent per days within 12 weeks.
 
If symptoms worsen or persist >1 week treat as grade 3.
 

		
 
• Report overdose and liver toxicity ECIs within 24 hours
 
• Withhold pembrolizumab
 
• Rule out bowel perforation
 
• Recommend gastroenterologist consult & biopsy with endoscopy
 
	
 
• methylprednisolone 125mg IV followed by prednisone 1 to 2 mg/kg/day or dexamethasone 4mg every 4 hours.
 
• Symptoms grade 1 or less initiate steroid taper for no less than 4 weeks.
 
• Taper 6-8 weeks in patients with diffuse or severe ulceration and/or bleeding
 
• If IV steroids do not reduce initial symptoms within 48-72 hours treat with additional anti-inflammatory measures. At symptom relief discontinue anti-inflammatory and initiate steroid taper over 45-60 days. If symptoms worsen during this period refer to Section 6 and 7.
 

			
 
• Manage as per grade 3
 

Endocrine – Hypo and hyperthyroidism	Grade 1 (Asymptomatic)	
 
• No action
 
	
 
• Intervention not indicated
 

	Grade 2 Hyperthyroidism and Grade 2- 4 Hypothyroidism	
 
• Report overdose and liver toxicity ECIs - see Section 6 and 7.
 
• Monitor thyroid function until returned to baseline.
 
• Consider consultation with endocrinologist.
 
• Pembrolizumab can continue while on this treatment.
 
	
 
• Thyroid hormone and/or steroid replacement therapy.
 
• Hyper – non-selective beta blockers for initial therapy
 
• Hypo – thyroid hormone replacement therapy as per standard of care.
 

	Grade 3 Hyperthyroidism	
 
• Report overdose and liver toxicity ECIs within 24 hours
 
• Withhold pembrolizumab, may restart if Grade 1 or resolved within 12 weeks
 
• Rule out infection and sepsis.
 
	
 
• IV methylprednisolone 1-2mg/kg followed by prednisone 1-2mg/kg per day.
 
• Symptoms grade 1 or less initiate steroid taper for no less than 4 weeks. Replacement of appropriate hormones may be required.
 
• Permanently discontinue pembrolizumab if dose cannot be reduced to prednisone 10mg or less or equivalent per day within 12 weeks.
 

	Grade 4 Hyperthyroidism	
 
• Report overdose and liver toxicity ECIs within 24 hours
 
• Discontinue pembrolizumab
 
	
 
• Manage as per grade 3
 

Endocrine – Hypophysitis or other symptomatic endocrinopathy	Grade 1 (Asymptomatic)	
 
• No action
 
	
 
• Intervention not indicated
 

	Grade 2 – 4	
 
• Report overdose and liver toxicity ECIs - see Section 6 and 7.
 
• Withhold pembrolizumab
 
	
 
• Prednisone 40mg p.o. or equivalent per day.
 
• Symptoms grade 1 or less initiate steroid taper for no less than 4 weeks. Replacement of appropriate hormones may be required.
 

		
 
Rule out infection and sepsis.
 
Monitor thyroid function until returned to baseline.
 
Consider pituitary gland imaging
 
Hypophysitis with clinically significant adrenal insufficiency and hypotension, dehydration, and electrolyte abnormalities (such as hyponatremia and hyperkalemia) constitutes adrenal crisis.
 
Consider endocrinologist consult.
 
	
 
Permanently discontinue pembrolizumab if dose cannot be reduced to prednisone 10mg or less or equivalent per day within 12 weeks.
 

Type 1 Diabetes Mellitus and ≥ grade 3 hyperglycaemia	Type 1 Diabetes Mellitus and ≥ grade 3 hyperglycaemia	
 
Report overdose and liver toxicity ECIs if appropriate see Section 6 and 7
 
Hold pembrolizumab if new onset of diabetes or grade 3-4 hyperglycaemia with evidence of beta cell failure.
 
Consultation with endocrinologist
 
Consider islet cell antibodies and antibodies to GAD, IA-2 ZnT8 and insulin.
 
	
 
Insulin replacement therapy is recommended for Type 1 diabetes mellitus and for Grade 3-4 hyperglycaemia associated with metabolic acidosis or ketonuria.
 
Evaluate patients with serum glucose and a metabolic panel, urine ketones, glycosylated haemoglobin, and C-peptide.
 

Haematologic	Grade 1 (Asymptomatic)	
 
No action
 
	
 
Intervention not indicated
 

	Grade 2	
 
Report overdose and liver toxicity ECIs within 24 hours
 
Withhold pembrolizumab, may restart if Grade 1 or resolved within 12 weeks
 
Consider Haematology consultation
 
	
 
Prednisone 1-2mg/kg daily
 
Permanently discontinue pembrolizumab if dose cannot be reduced to prednisone 10mg or less or equivalent per day within 12 weeks.
 

	Grade 3	
 
Report overdose and liver toxicity ECIs within 24 hours
 
Withhold pembrolizumab, may restart if Grade 1 or resolved within 12 weeks
 
Recommend Haematology consultation
 
	
 
IV methylprednisolone 125mg or Prednisone 1-2mg/kg p.o. (or equivalent) as appropriate.
 
Permanently discontinue pembrolizumab if corticosteroid dose cannot be reduced to prednisone 10mg or less or equivalent per day within 12 weeks.
 

	Grade 4	
 
• Report overdose and liver toxicity ECIs within 24 hours
 
• Discontinue pembrolizumab
 
• Recommend Haematology consultation
 
	
 
• IV methylprednisolone 125mg or Prednisone 1-2mg/kg p.o. (or equivalent) as appropriate.
 

Hepatic – Drug induced Liver Injury (DILI).  Please refer to Section 6 and 7 for definitions of (DILI)	Grade 1 (Asymptomatic)	
 
• No action
 
	
 
• Intervention not indicated
 

	Grade 2	
 
• Report overdose and liver toxicity ECIs within 24 hours
 
• Withhold Pembrolizumab if AST or ALT >3.0 to 5.0 X ULN and/or total bilirubin is >1.5 to 3.0 X ULN
 
• Monitoring Liver function until values return to baseline
 
	
 
• 0.5-1mg/kg/day methylprednisolone 125mg or oral equivalent.
 
• LFT grade 1 or less initiate steroid taper for no less than 4 weeks. Consider prophylactic antibiotics and resume pembrolizumab.
 
• Permanently discontinue pembrolizumab if dose cannot be reduced to prednisone 10mg or less or equivalent per day within 12 weeks.
 
• Permanently discontinue pembrolizumab for patients with liver mets who begin treatment with grade 2 elevation of AST or ALT and AST or ALT increase ≥50% relative to baseline and lasts ≥ 1 week.
 

	Grade 3	
 
• Report overdose and liver toxicity ECIs within 24 hours
 
• Discontinue pembrolizumab if AST or ALT > 5.0 X ULN and/or total bilirubin is >3.0 X ULN
 
• Consider consultation and biopsy to establish aetiology
 
	
 
• High dose IV glucocorticosteroids for 24-48hours.
 
• Symptoms grade 1 or less initiate steroid taper for no less than 4 weeks 
 
◦ prednisone 1 to 2 mg/kg/day or dexamethasone 4mg every 4 hours.
 
 
 
• If serum transaminase levels do not decrease or symptoms worsen please refer to Section 6 and 7.
 
• Permanently discontinue pembrolizumab if dose cannot be reduced to prednisone 10mg or less or equivalent per day within 12 weeks.
 

	Grade 4	
 
• Report overdose and liver toxicity ECIs within 24 hours
 
• Discontinue pembrolizumab
 
	
 
• Manage as per grade 3
 

Neurologic	Grade 1 (Asymptomatic)	
 
• No action
 
	
 
• Intervention not indicated
 

	Grade 2	
 
• Report overdose and liver toxicity ECIs within 24 hours
 
• Consider withholding pembrolizumab
 
• Consider Neurology consult and biopsy for diagnosis.
 
	
 
• Consider 1-2mg/kg daily of prednisone as appropriate
 
• Permanently discontinue pembrolizumab if dose cannot be reduced to prednisone 10mg or less or equivalent per day within 12 weeks.
 

	Grade 3 and 4	
 
• Report overdose and liver toxicity ECIs within 24 hours
 
• Discontinue pembrolizumab
 
• Obtain Neurology consultation
 
	
 
• 1-2mg/kg daily of prednisone or equivalent.
 
• If condition worsens consider IVIG or other immunosuppressive therapies
 
• Symptoms grade 1 or less, initiate steroid taper for no less than 4 weeks.
 

		
 
Consider biopsy for diagnosis.
 
	
Ocular	Grade 1 (Asymptomatic)	
 
No action
 
	
 
Intervention not indicated
 

	Grade 2	
 
Report overdose and liver toxicity ECIs within 24 hours
 
Evaluation by ophthalmologist recommended
 
	
 
Topical steroids – 1%prednisolone acetate suspension and iridocyclitics
 
Permanently discontinue IF symptoms persist despite treatment.
 

	Grade 3	
 
Report overdose and liver toxicity ECIs within 24 hours
 
Evaluation by ophthalmologist recommended
 
Withhold pembrolizumab & consider discontinuation.
 
	
 
1-2mg/kg of prednisone daily.
 
Symptoms grade 1 or less initiate steroid taper for no less than 4 weeks.
 
Permanently discontinue pembrolizumab if dose cannot be reduced to prednisone 10mg or less or equivalent per day within 12 weeks.
 

	Grade 4	
 
Report overdose and liver toxicity ECIs within 24 hours
 
Evaluation by ophthalmologist recommended
 
Permanently discontinue pembrolizumab
 
	Manage as per grade 3
Renal	Grade 1 (Asymptomatic)	
 
No action
 
	
 
Intervention not indicated
 

	Grade 2	
 
Report overdose and liver toxicity ECIs within 24 hours
 
Withhold Pembrolizumab
 
	
 
1-2mg/kg of prednisone daily.
 
Permanently discontinue pembrolizumab if dose cannot be reduced to prednisone 10mg or less or equivalent per day within 12 weeks.
 

	Grade 3 and 4	
 
Report overdose and liver toxicity ECIs within 24 hours
 
Discontinue Pembrolizumab
 
Renal consultation and biopsy as appropriate
 
	
 
1-2mg/kg of prednisone daily.
 
Symptoms grade 1 or less initiate steroid taper for no less than 4 weeks.
 

Skin – Rash and pruritus	Grade 1 (Asymptomatic)	
 
No action
 
	
 
Intervention not indicated
 

	Grade 2	
 
Symptomatic treatment
 
	
 
Topical glucocorticosteroids or urea-containing cream in combination with oral anti-pruritics
 
Treatment with oral steroids at PIs discretion
 

	Grade 3	
 
Report overdose and liver toxicity ECIs within 24 hours
 
Withhold Pembrolizumab
 
Consider dermatology consult & biopsy for diagnosis.
 
	
 
1mg/kg/day prednisone or equivalent or dexamethasone 4mg 4xdaily
 
Symptoms grade 1 or less, initiate steroid taper for no less than 4 weeks.
 
Permanently discontinue pembrolizumab if dose cannot be reduced to prednisone 10mg or less or equivalent per day within 12 weeks.
 

	Grade 4	
 
Report overdose and liver toxicity ECIs within 24 hours
 
	
 
Initiate steroids starting with 1-2mg/kg prednisone or equivalent..
 

		
hours
 
 
• Discontinue pembrolizumab
 
• Dermatology consultation
 
• Consider biopsy for diagnosis & clinical photographs
 
	
 
• Symptoms grade 1 or less, initiate steroid taper for no less than 4 weeks.
 

Skin – Dermatitis exfoliative, erythema multiforme, Stevens Johnson syndrome§, toxic epidermal necrolysis§.
 
§ If it is suspected that the patient has SJS or TEN, pembrolizumab should be withheld. The patient should be referred to a dermatologist for management. If SJS and TEN is confirmed, then pembrolizumab should be permanently discontinued.”
	Grade 1 (Asymptomatic)	
 
• No action
 
	
 
• Intervention not indicated
 

	Grade 2	
 
• Report overdose and liver toxicity ECIs within 24 hours
 
• Symptomatic treatment
 
	
 
• Topical glucocorticosteroids or urea-containing cream in combination with oral anti-pruritics. Treatment with oral steroids at PIs discretion
 

	Grade 3	
 
• Report overdose and liver toxicity ECIs within 24 hours
 
• Withhold Pembrolizumab
 
• Consider dermatology consultation and biopsy for diagnosis.
 
	
 
• 1mg/kg/day prednisone or equivalent or dexamethasone 4mg 4xday.
 
• Symptoms grade 1 or less initiate steroid taper for no less than 4 weeks.
 
• Permanently discontinue pembrolizumab if dose cannot be reduced to prednisone 10mg or less or equivalent per day within 12 weeks.
 

	Grade 4	
 
• Report overdose and liver toxicity ECIs within 24 hours
 
• Discontinue pembrolizumab
 
• Dermatology consultation
 
• Consider biopsy for diagnosis & clinical photographs
 
	
 
• Initiate steroids starting with 1-2mg/kg prednisone or equivalent..
 
• Symptoms grade 1 or less, initiate steroid taper for no less than 4 weeks.
 


Other:
 
 
• Myocarditis¶
 
• Pericarditis
 
• Pancreatitis
 
• Any additional Grade 3 or higher event which the physician considers to be immune related
 
 
¶ Ensure that other causes of myocarditis are adequately evaluated to exclude other aetiologies
	Grade 2 or Grade 1 that do not improve with symptomatic treatment.	
 
• Report overdose and liver toxicity ECIs within 24 hours
 
• Withhold Pembrolizumab
 
• Consider biopsy for confirmation of diagnosis.
 
	
 
• Systemic corticosteroids may be indicated.
 
• If so:
 
• Treat with systemic corticosteroids at a dose of 1 to 2 mg/kg prednisone or equivalent once per day.
 
• When symptoms improve to Grade 1 or less, steroid taper should be started and continued over no less than 4 weeks.
 
• Permanently discontinue for inability to reduce corticosteroid dose to 10 mg or less of prednisone or equivalent per day within 12 weeks. Otherwise, Pembrolizumab treatment may be restarted and the dose modified as specified in the protocol
 

	Grade 3	
 
• Report overdose and liver toxicity ECIs within 24 hours
 
• Withhold Pembrolizumab
 
	
 
• Treat with systemic corticosteroids at a dose of 1 to 2 mg/kg prednisone or equivalent once per day.
 
• When symptoms improve to Grade 1 or less, steroid taper should be started and continued over no less than 4 weeks.
 
• Permanently discontinue for inability to reduce corticosteroid dose to 10 mg or less of prednisone or equivalent per day within 12 weeks. Otherwise, pembrolizumab treatment may be restarted and the dose modified as specified in the protocol
 

	Grade 4	

• Report overdose and liver toxicity ECIs within 24 hours

• Discontinue pembrolizumab

	

• Treat with systemic corticosteroids at a dose of 1 to 2 mg/kg prednisone or equivalent once per day.

--	---------	--	--

